4.6.3.2 Presentations

Only on treatment laboratory data as defined in Section [3.3.2.3](#) are included in the summary tables. The same section describes the treatment period definitions and provides further information on the presentation of the tables. Haematology and clinical chemistry data will be summarised by treatment group and scheduled visit using descriptive statistics over time in terms of absolute values and changes from baseline for each treatment period.

Shift tables showing CTCAE grades from baseline to worst CTCAE grade on treatment will be produced for each treatment period for parameters with available CTCAE grades (see [Table 17](#)). Hyper- and/or hypo-directionality will be indicated in the parameter's labels. Percentages are based on the number of patients with a baseline value and an on-treatment value.

For parameters in [Table 17](#) with no CTCAE grading (“No” for CTCAE grading available), the number and percentage of patients with any on treatment increase from baseline, any on treatment decrease from baseline, and a TELC is summarised. Percentages are based on the

number of patients with a baseline value below/above the local laboratory upper/lower reference limit and an on-treatment value for the any increase/decrease summaries, respectively. Percentages for a TELC are based on the number of patients with a baseline value and an on-treatment value.

Haematology and clinical chemistry data in [Table 17](#) will also be presented graphically for each treatment period using boxplots for absolute values and changes from baseline by scheduled visit.

A table will be provided for patients with potential Hy's law (alanine aminotransferase [ALT] or aspartate aminotransferase [AST] $\geq 3 \times$ upper limit of normal [ULN], and total bilirubin $\geq 2 \times$ ULN), where the onset date of ALT or AST elevation is prior to or on the date of total bilirubin elevation.

Laboratory data for the variables listed in the CSP Table 8 will be listed. Site reference ranges will also be listed. Flags (H or L) will be applied to values falling outside the reference ranges (which will be explicitly noted on these listings where applicable), and for the CTCAE grade for parameters for which CTCAE grading applies.

4.6.4 Clinical Laboratory, Urinalysis

4.6.4.1 Definitions and Derivations

Urine samples for determination of urinalysis are collected as described in the CSP.

The rules described in Sections [3.3.1](#), [3.3.3](#), [3.3.4](#), and [3.3.5](#) of this document considering definition of baseline, visit windows, and handling multiple records and records above or below the limit of quantification are followed.

4.6.4.2 Presentations

Urinalysis data will only be listed, and no summary tables will be produced. Site reference ranges will also be listed. Flags (H or L) will be applied to values falling outside the reference ranges (which will be explicitly noted on these listings where applicable), and to values for which CTCAE grading applies.

4.6.5 Other Laboratory Evaluations

4.6.5.1 Definitions and Derivations

Pregnancy tests (serum at screening, and serum or urine at other timepoints) will be performed for women of childbearing potential.

4.6.5.2 Presentations

Pregnancy test data will only be listed, and no summary tables will be produced.

4.6.6 Vital Signs

4.6.6.1 Definitions and Derivations

Vital signs will be assessed at timelines specified in the CSP.

The rules described in Sections 3.3.1, 3.3.3, and 3.3.4 of this document considering definition of baseline, visit windows, and how to handle multiple records are followed.

4.6.6.2 Presentations

Only on-treatment vital signs data as defined in Section 3.3.2.3 are included in the summary tables. The same section describes the treatment period definitions and further information on the presentation of the tables.

All vital signs (temperature, systolic and diastolic blood pressure, pulse rate, respiratory rate, and oxygen saturation) and growth parameters (weight and BSA) will be summarised using descriptive statistics over time in terms of absolute values and change from baseline by treatment group and scheduled visit for each treatment period. As per the schedule of assessments in the CSP, height will only be summarised at baseline in the table of descriptives; however, all available data will be listed. Baseline for this parameter will be calculated using screening assessment. If this value is unavailable, then the last value before first dose on Cycle 1 Day 1 will be used.

Vital signs data will also be presented graphically for each treatment period using boxplots for absolute values and changes from baseline by treatment group and scheduled visit.

All vital signs data will be listed.

4.6.7 Electrocardiogram

4.6.7.1 Definitions and Derivations

12-lead ECGs will be recorded at visits specified in the CSP.

The rules described in Sections 3.3.1, 3.3.3, and 3.3.4 of this document considering definition of baseline, visit windows, and handling multiple records are followed.

For ECGs taken on the same day in triplicate, the average of the three readings is calculated.

The overall evaluation of an ECG is either “normal” or “abnormal”, with abnormalities categorised as either “clinically significant” or “not clinically significant”. For ECGs taken on the same day in triplicate, the worse evaluation will be selected, i.e. “abnormal” versus “normal” and “clinically significant” versus “not clinically significant”.

4.6.7.2 Presentations

A summary table of absolute values will be presented for baseline.

A frequency table showing the number of patients with their interpretation of the ECG reading (normal; abnormal, clinically not significant; and abnormal, clinically significant) at baseline by treatment group will be presented.

All ECG data will be listed.

4.6.8 Echocardiogram/Cardiac MRI

4.6.8.1 Definitions and Derivations

An echocardiogram (ECHO) or cardiac MRI scan to assess left ventricular ejection fraction (LVEF), end diastolic, and end systolic left ventricular volumes will be performed at visits specified in the CSP.

The rules described in Sections [3.3.1](#), [3.3.3](#), and [3.3.4](#) of this document considering definition of baseline, visit windows, and handling multiple records are followed.

4.6.8.2 Presentations

Only on-treatment laboratory data as defined in Section [3.3.2.3](#) are included in the summary tables. The same section describes the treatment period definitions and further information on the presentation of the tables.

A summary table of absolute values and change from baseline of LVEF, end diastolic, and end systolic left ventricular volumes will be presented by treatment group and scheduled visit for each treatment period.

For ejection fraction decrease, a shift table showing CTCAE grades from baseline to maximum on-treatment will be produced for each treatment period.

All ECHO and cardiac MRI data will be listed.

4.6.9 Ophthalmologic Assessments

4.6.9.1 Definitions and Derivations

An ophthalmologic examination (best corrected visual acuity, intraocular pressure, and slit-lamp fundoscopy) will be evaluated at the times outlined in the CSP and as clinically indicated whilst the patient is on study intervention.

The rules described in Sections [3.3.1](#), [3.3.3](#), and [3.3.4](#) of this document considering definition of baseline, visit windows, and handling multiple records are followed.

4.6.9.2 Presentations

Only intraocular pressure will be presented graphically using box plots for absolute values and changes from baseline by treatment group and scheduled visits for each treatment period, split by right eye and left eye within the same plot.

Only on-treatment ophthalmologic examination data as defined in Section 3.3.2.3 are included in the figure. The same section describes the treatment period definitions and further information on the presentation of the tables.

Ophthalmology examination data will be listed for patients, including a description of the abnormalities and relevant baseline result.

4.6.10 Physical Examinations

4.6.10.1 Definitions and Derivations

A full physical examination will be performed at screening and baseline, including assessments of the following: general appearance, respiratory, cardiovascular, abdomen, skin, head and neck (including ears, eyes, nose, and throat), lymph nodes, thyroid, musculoskeletal (including spine and extremities), urogenital, dermatological, gastrointestinal, endocrine, haematologic/lymphatic, and neurological systems. Targeted physical examinations will be performed at subsequent visits and will include, at a minimum, assessments of the general appearance, respiratory and cardiovascular systems, skin, and abdomen (liver and spleen).

4.6.10.2 Presentations

Physical examination data will be listed, including a description of the abnormalities and relevant baseline findings.

4.6.11 ECOG Performance Status

4.6.11.1 Definitions and Derivations

An assessment of ECOG performance status score will be performed at the visits as shown in the CSP.

The ECOG performance status scores range from 0 to 5, with lower scores indicating greater patient activity:

- 0 Fully active; able to carry out all usual activities without restrictions.
- 1 Restricted in strenuous activity, but ambulatory and able to carry out light work or work of a sedentary nature (e.g., light housework or office work).
- 2 Ambulatory and capable of self-care, but unable to carry out any work activities; up and about more than 50% of waking hours.

3 Capable of only limited self-care; confined to bed or chair more than 50% of waking hours.

4 Completely disabled; unable to carry out any self-care and totally confined to bed or chair.

5 Dead

The rules described in Sections [3.3.1](#), [3.3.3](#), and [3.3.4](#) of this document considering definition of baseline, visit windows, and handling multiple records are followed.

4.6.11.2 Presentations

A shift table showing each category from baseline to maximum on-treatment record will be produced for each treatment period.

Only on-treatment ECOG data as defined in Section [3.3.2.3](#) are included in the shift table. The same section describes the treatment period definitions and further information on the presentation of the tables.

The ECOG performance status at each visit indicated in the SoA will be listed.

5 INTERIM ANALYSIS

The interim analysis (DCO1) is expected to occur after the 100th randomised patient has had the opportunity to complete their end of Cycle 16 assessment. This corresponds to approximately 68.5% of the primary endpoint information expected at the primary analysis (DCO2). As it is expected that all 145 patients will have completed Cycle 12 by the time the 100th randomised patient has completed Cycle 16, the information fractions for the key secondary endpoints are estimated to be 100% at the interim analysis. See Section [3.3.7](#) for details on the multiplicity testing approach.

The interim analyses will be performed by a team of unblinded statisticians and programmers independent from AstraZeneca and reviewed by an Unblinded Review Committee. If the URC recommends the study team to be unblinded, the results of these analyses may form the basis of submissions for regulatory approval. If the interim analysis DCO (DCO1) is due to take place within approximately 4 months of the primary analysis DCO (DCO2), then the interim analysis may not be performed and only the primary analysis will be performed.

For further details of the interim analysis including which outputs will be provided to the URC, please refer to the URC Charter and the Interim Analysis SAP.

7 APPENDIX 1 – ANALYSIS OF DATA FROM JAPAN

7.1 Introduction

To support registration in Japan, in addition to the evaluation of the global study data for primary, secondary and safety objectives, evaluation of consistency in efficacy and safety in the Japanese population is required to facilitate the benefit-risk assessment for Japanese patients. The Japan subpopulation analyses will not be part of the CSR.

This appendix outlines the pre-specified analyses of study D134BC00001 to be conducted for the Japan subpopulation.

7.1.1 Definition of Japan Subpopulation

The Japan subpopulation will include all patients enrolled at sites in Japan.

7.2 Analysis Sets

The definition of the analysis sets for the Japan subpopulation will be the same as the global study but including only patients enrolled in Japan. Definitions of analysis sets for DCO1 are provided in Section 2.2 of the interim SAP. Definitions of analysis sets for DCO2 and final DCO are provided in Section 3.2 of the main study SAP.

Analysis sets for Japan subpopulation analysis include the following:

- Japan-only enrolled subjects
- Japan-only FAS
- Japan-only pain FAS
- PK analysis set (Japanese subpopulation vs non-Japanese subpopulation)
- Japan-only randomised period SAF
- Japan-only on-selumetinib SAF

The analysis sets used for each outcome will also be the same as defined in Section 3.2.11 of the main study SAP.

7.3 Analysis Variables

Endpoints for the Japan subpopulation include the following:

- Study population:
 - Subject disposition
 - Demographic characteristics, subject characteristics, and disease characteristics at baseline
- REiNS-related efficacy:
 - Objective response rate (ORR) by end of Cycle 16, on-treatment MRI volumetric assessments period for comparison of selumetinib vs placebo

- Actual value and change from baseline in target PN volume over time
- Other efficacy:
 - Actual value and change from baseline in PAINS-pNF chronic target PN pain intensity scores over time
 - Mean change from baseline in PAINS-pNF chronic target PN pain intensity scores over randomised period
 - Mean change from baseline in PlexiQoL total score over the randomised period
- Pharmacokinetic:
 - Summary of plasma concentrations of selumetinib and N-desmethyl selumetinib for multiple dose Cycle 1, Day 8 (Japanese subpopulation vs non-Japanese subpopulation)
 - Combined individual plasma concentrations of selumetinib versus time and N-desmethyl selumetinib versus time for multiple dose Cycle 1, Day 8 (Japanese subpopulation vs non-Japanese subpopulation) (linear and semi-logarithmic scales)
 - Summary of pharmacokinetic parameters of selumetinib and N-desmethyl selumetinib for multiple dose Cycle 1, Day 8 (Japanese subpopulation vs non-Japanese subpopulation)
- Safety:
 - Duration of exposure
 - Treatment-emergent adverse events (AE) as follows: (i) in any category; (ii) by system organ class (SOC) and preferred term (PT); (iii) assessed by investigator as possibly related to study intervention by SOC and PT; (iv) CTCAE grade 3 or higher by SOC and PT; (v) with outcome of death by SOC and PT
 - Adverse events of special interest
 - Treatment-emergent serious adverse events (TEAE) as follows: (i) by SOC and PT; (ii) leading to discontinuation of study intervention by SOC and PT

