4.2.2 Key Secondary Endpoints

4.2.2.1 PAINS-pNF chronic target PN pain intensity score

4.2.2.1.1 Definition

The 1st key secondary estimand is the difference of the means in the change from baseline in PAINS-pNF chronic target PN pain intensity score at Cycle 12 between selumetinib and placebo amongst patients with a PAINS-pNF chronic target PN pain intensity score ≥ 3 at baseline (Pain FAS) and at least one post-baseline average cycle PAINS-pNF chronic target PN pain intensity score.

The randomised period is defined in Section [3.3.2.2](#).

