4.2.2.1.7 Supplementary Analyses of the 1st Key Secondary Endpoint

Additionally, PAINS-pNF chronic target PN pain intensity actual scores as well as the change from baseline at each cycle will be summarised descriptively by visit and study intervention arm for FAS and Pain FAS. If there are instances of early crossover, then some cycles prior to Cycle 12 will summarise data of placebo subjects who have already crossed over to selumetinib.

Summary statistics will include n, mean, standard deviation, min, Q1, median, Q3, and max, where n is the number of subjects contributing to the summary statistics for the visit.

This descriptive analysis in the Pain FAS will be repeated only for the randomised period by considering the three missing cycle score rules mentioned in Section [4.2.2.1.6](#).

Summary statistics will also be presented by attributable versus non-attributable reasons (see Section [3.3.9](#)) only for the randomised period.

Plots of the mean scores, as well as the changes from baseline and the associated 95% CIs by cycle will be produced for the randomised period.

The empirical cumulative distribution function (eCDF) of change from baseline by study intervention arm will be plotted at Cycle 12 for the Pain FAS. The eCDF will be the cumulative percent frequency (Cum_Pct) of the change from baseline in the PAINS-pNF chronic target PN pain intensity actual score by study intervention arm saved by default in the output dataset of the SAS procedure proc freq.

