The waterfall plot and histograms will be summarised and analysed using a subset of the FAS including patients with measurable target PN at baseline per ICR who received at least one dose of study intervention and had at least one post-baseline target PN volume during the randomised period.

The analysis will be repeated using the same method but will not be restricted to the randomised period using the Selumetinib FAS.

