7.5 TFLs for Japan Subpopulation

Details of the specific analyses to be performed for the Japan subpopulation are presented in [Table 18](#).

Table 18 TFLs for Japan subpopulation

Type	Title	Additional Notes
Table	Subject disposition (Japanese)	
 Japan-only enrolled patients
Table	Demographic characteristics (Japanese)	
 Japan-only FAS
Table	Subject characteristics (Japanese) ^a	
 Japan-only FAS
Table	Disease characteristics at baseline (Japanese)	
 Japan-only FAS
Table	Objective response rate by end of Cycle 16, primary analysis, on-treatment MRI volumetric assessments period (Japanese)	
 Japan-only FAS p-value not to be displayed
Table	Target PN volume, actual value and change from baseline (Japanese)	
 Japan-only FAS
Table	PAINS-pNF chronic target PN pain intensity scores: actual value and change from Baseline (Japanese)	
 Japan-only pain FAS
Table	PlexiQoL total scores over time: actual value and change from Baseline (Japanese)	
 FAS
Table	Summary of plasma concentrations (ng/mL) of selumetinib - Multiple dose Cycle 1, Day 8 (Japanese)	
 PK analysis set – Japan subpopulation
Table	Summary of plasma concentrations (ng/mL) of selumetinib - Multiple dose Cycle 1, Day 8 (non-Japanese)	
 PK analysis set - non-Japan subpopulation
Table	Summary of plasma concentrations (ng/mL) of N-desmethyl selumetinib - Multiple dose Cycle 1, Day 8 (Japanese)	
 PK analysis set – Japan subpopulation
Table	Summary of plasma concentrations (ng/mL) of N-desmethyl selumetinib - Multiple dose Cycle 1, Day 8 (non-Japanese)	
 PK analysis set - non-Japan subpopulation
Figure	Combined individual plasma concentrations (ng/mL) of selumetinib versus time - Multiple dose Cycle 1, Day 8 (linear scale) (Japanese vs non-Japanese)	
 PK analysis set - Japan and non-Japan subjects to be displayed on the same plot using different colours for each subpopulation

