8.3 Analysis Variables

Endpoints for the China subpopulation include the following:

- Study population:
 - Subject disposition
 - Analysis sets
 - Protocol deviations

- Demographic characteristics at baseline
- Subject characteristics and disease characteristics at baseline
- Medical history and previous PN-directed treatment modalities and medical treatments
- Prior medications, allowed and disallowed concomitant medications during the randomised period, allowed and disallowed concomitant medications during the on-selumetinib period
- Distribution of eDiary entries for the following: PAINS-pNF chronic target PN pain; PN pain medication
- Instrument completion rate for PlexiQoL
- REiNS-related efficacy:
 - Objective response rate (ORR) by end of Cycle 16, on-treatment MRI volumetric assessments period for comparison of selumetinib vs placebo
 - Actual value, change from baseline and percentage change from baseline in target PN volume over time
 - Single-arm ORR, best objective response (BOR), duration of response (DOR), progression-free survival (PFS), time to progression (TTP) and time to response (TTR)
 - PFS during randomised period
 - Best percentage change from baseline in target PN volume during randomised period and on-treatment MRI volumetric assessments period
- Other efficacy:
 - Actual value, change from baseline and mean scores for PAINS-pNF chronic target PN pain intensity scores over time
 - Mean change from baseline in PAINS-pNF chronic target PN pain intensity scores over randomised period
 - Actual value and change from baseline in PlexiQoL total scores over time
 - Mean change from baseline for PlexiQoL total score over randomised period
 - Chronic target PN pain palliation and time to chronic target PN pain palliation during randomised period
 - Chronic PN pain medication: strongest analgesic ladder class and score by cycle; change from baseline
 - Decrease in pain medication over the randomised period, as reported in the e-Diary and as reported by investigator
 - Distribution of Patient Global Impression of Severity (PGIS) and Patient Global Impression of Change (PGIC) over time and shift in PGIS responses at cycle 12

- Pharmacokinetic:
 - Summary of plasma concentrations of selumetinib and N-desmethyl selumetinib for multiple dose Cycle 1, Day 8 (Chinese subpopulation vs non-Chinese subpopulation)

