Figure	Target PN volume, best percentage change during the randomised period, waterfall plot (Chinese)	China-only FAS
Figure	Target PN volume, best percentage change during the randomised period, histogram (Chinese)	China-only FAS
Figure	Target PN volume, best percentage change during the on-treatment MRI volumetric assessments period, waterfall plot (Chinese)	China-only FAS
Figure	Target PN volume, best percentage change during the on-treatment MRI volumetric assessments period, histogram (Chinese)	China-only FAS
Table	Proportion of cycles during the randomised period with chronic target pain palliation - Primary definition (Chinese)	China-only pain FAS
Table	Time to first chronic target PN pain palliation during the randomised period (Chinese)	China-only pain FAS
Figure	Time to first chronic target PN pain palliation during the randomised period, Kaplan-Meier plot (Chinese)	China-only pain FAS

Table 19 TFLs for China subpopulation

Table	Chronic PN pain medication strongest analgesic ladder class and score by cycle (Chinese)	China-only FAS
Table	Change from baseline in chronic PN pain medication (Chinese)	China-only FAS
Table	Change from baseline in chronic PN pain medication (Chinese)	China-only pain FAS
Table	Proportion of cycles during the randomised period with pain medication decrease as reported in the e-Diary (Chinese)	China-only FAS
Table	Proportion of cycles during the randomised period with pain medication decrease as reported by the investigator (Chinese)	China-only FAS
Figure	Progression free survival during the randomised period, Kaplan-Meier plot, primary analysis, on-treatment MRI volumetric assessments period (Chinese)	China-only FAS
Table	Progression free survival during the randomised period, primary analysis, on-treatment MRI volumetric assessments period (Chinese)	China-only FAS
Table	Distribution of Patient Global Impression of Severity (PGIS) responses over time (Chinese)	China-only FAS
Table	Distribution of Patient Global Impression of Change (PGIC) responses over time	China-only FAS
Table	Shift table of Patient Global Impression of Severity (PGIS) responses at Cycle 12 (Chinese)	China-only FAS
Table	Summary of plasma concentrations (ng/mL) of selumetinib - Multiple dose Cycle 1, Day 8 (Chinese)	PK analysis set – Chinese subpopulation
Table	Summary of plasma concentrations (ng/mL) of selumetinib - Multiple dose Cycle 1, Day 8 (non-Chinese)	PK analysis set - non-Chinese subpopulation

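### Some regional output rows do not match the main SAP: Japan has no between-arm estimate for either key secondary endpoint, and three China rows use a different population

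*SAP*

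**What the plan says.** The first key secondary estimand (SAP 4.2.2.1.1) is the difference of means in the "change from baseline in PAINS-pNF chronic target PN pain intensity score at Cycle 12 between selumetinib and placebo". SAP 4.2.2.2.5 sets the same timing for PlexiQoL, in FAS participants with a baseline score and at least one later score. Both are estimated by MMRM. The model also reports every other cycle and a period average, all nominal.

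For Japan, SAP 7.3 lists "Mean change from baseline in PAINS-pNF chronic target PN pain intensity scores over randomised period" and the corresponding PlexiQoL item. SAP 7.4 says that results come with a 95% CI and no p-value, that no sensitivity or supplementary analyses are planned, and that the outputs are those in 7.5. In Table 18 the only PAINS-pNF row is "PAINS-pNF chronic target PN pain intensity scores: actual value and change from Baseline (Japanese") and the only PlexiQoL row is "PlexiQoL total scores over time: actual value and change from Baseline (Japanese"), the latter on a set given simply as FAS.

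For China, SAP 8.3 lists "Mean change from baseline for PlexiQoL total score over randomised period" and a matching PAINS-pNF item. Table 19 does include a model table for each, labelled as the primary analysis. It also includes "Target PN volume, best percentage change during the on-treatment MRI volumetric assessments period, waterfall plot (Chinese") and a matching histogram, both on the China-only FAS. The global counterpart in SAP 4.2.8.5 is an analysis that "will not be restricted to the randomised period using the Selumetinib FAS".

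**The concern.** Both appendices state that consistency of efficacy in the region has to be evaluated to support registration. That needs the same quantity, in the same population, as the global analysis.

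For Japan, by-arm descriptive values give neither a treatment difference nor an interval to set beside the global estimate. They also do not follow the estimand's handling of early crossover: SAP 4.2.2.1.7 warns that "some cycles prior to Cycle 12 will summarise data of placebo subjects who have already crossed over to selumetinib", and 4.2.2.2.7 says the same for PlexiQoL.

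For China, a plot of best change that runs past Cycle 12 in both arms credits the placebo arm with shrinkage that may have occurred on selumetinib. A PlexiQoL primary table on the pain subset answers the question for a narrower population than the global one.

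**Working it through.** The plan states no figure on this point, so there is nothing to reproduce. The check sets the rows side by side, with one count of scans and one proportion.

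**Japan, key secondary endpoints**

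- SAP 7.3 has three relevant items: PAINS-pNF values and changes over time, PAINS-pNF mean change, and PlexiQoL mean change.
- Table 19 titles China's two model tables in almost the same words as the mean-change items and labels them as the primary analysis. The mean-change items in 7.3 therefore most naturally correspond to the MMRM of 4.2.2.1.5 and 4.2.2.2.5.
- Table 18 has a row for the first item only. Neither mean-change item has a row, and the PlexiQoL row that is present matches nothing in 7.3.
- In the main SAP the descriptive summaries are supplementary analyses (4.2.2.1.7 and 4.2.2.2.7). Table 18 keeps these and omits the primary analysis, although 7.4 says no supplementary analyses are planned.
- SAP Tables 9 and 10 set scores after early crossover to missing. The descriptive summaries can include them.
- Of the three endpoints in SAP 3.3.7, only ORR by end of Cycle 16 has a Japan row that yields a between-arm estimate (the risk difference of 4.2.1.9). The other 2 of 3 have none.

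**China, whole-period waterfall and histogram**

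- Population: Selumetinib FAS in 4.2.8.5; China-only FAS, so both arms, in Table 19.
- Window: SAP 3.3.2.1 runs from first dose of study intervention to discontinuation or data cut-off. It does not stop at crossover.
- Exclusions: 4.2.8.3 follows Table 8, whose footnote limits the crossover event to crossover before Cycle 12 for progression. The scheduled switch after Cycle 12 removes no scans. SAP 3.4 agrees: it justifies a 0% placebo ORR by saying that a response after crossover would still be unconfirmed, not that the scan is ignored.
- Best change (4.2.8.2) needs no confirmation, so a single scan after crossover can set a placebo bar.
- Scans are scheduled at Cycles 4, 8, 12, 16, 20 and 24. For a placebo participant who switches on schedule and stays on treatment, those at 16, 20 and 24 are on selumetinib:
  - by Cycle 16: 1/4 = 25%
  - by Cycle 20: 2/5 = 40%
  - by Cycle 24: 3/6 = 50%
- SAP 8.4 times the China analysis at the first global data cut-off, so the share for each participant depends on when that participant was randomised.

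**PlexiQoL analysis sets**

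- Global primary analysis: FAS subset (4.2.2.2.5). SAP Table 1 marks the Pain FAS as supplementary.
- China primary-analysis table: China-only pain FAS. China LS-mean figure: China-only FAS. SAP 8.2 says the sets are as in 3.2.11.
- Japan row: FAS, without the Japan-only prefix used on the neighbouring efficacy rows.
- Size: if China's mix followed the global caps of about 106 and 40, the pain subset would leave out 40/(106 + 40) = 40/146 = 27% of participants. The documents give no regional breakdown, so this is only a guide.

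**The case against.** The strongest reply is that everything here is exploratory (Japan, 7.4) or non-inferential (China, 8.4), so by-arm descriptive tables are a defensible choice for a small region. In 7.3 only the ORR item is expressly described as a comparison. The plain FAS label on the Japan PlexiQoL row is harmless, because its title says Japanese and 7.2 restricts every set to Japan. Early crossover applies only to progression confirmed by central review and may be rare. SAP 7.4 also refers to output lists in the interim SAP, which was not available. Most of this stands and keeps the point small. It does not explain why 7.3 lists items that 7.5 never delivers, or why China receives the model tables and Japan does not.

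A reader might go further and infer that both regions will report the period average in place of the Cycle 12 effect, and so see a shrunken effect. The documents do not support that. The wording in 7.3 and 8.3 omits Cycle 12, but it does not clearly mean only the average. China's model tables are labelled primary analysis and inherit an MMRM that reports Cycle 12. The global model also reports the average, so a like-for-like comparison would exist either way. Any shrinkage figure would rest on an assumed onset profile that the plan does not give.

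A reader might also infer that the China plots would make the arms look alike. Table 19 has randomised-period versions of both plots, which show the arms before the scheduled crossover, so that inference fails.

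**Conclusion.** Three mismatches hold on the text. Japan has no between-arm estimate or interval for either key secondary endpoint. Two China whole-period plots include placebo participants whose best change may come from scans on selumetinib. The PlexiQoL sets are inconsistent, materially for China and only as a label for Japan. The absence of Cycle 12 from the regional wording is unclear labelling, not evidence that the estimate will be missing. It would also be wrong to say that the appendices fail to mirror the global analyses in general: ORR by end of Cycle 16 is carried over as the primary analysis in both regions, and China has model tables for both key secondary endpoints.

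The conclusion assumes that Table 18 is the full Japan list, as 7.4 and 7.5 say. The scan shares assume on-schedule crossover and no discontinuation. The global confirmatory tests are untouched, so severity is minor. The changes still affect what the regional consistency check can show.

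**What to change.** - Table 18: add the MMRM treatment-difference tables, giving the Cycle 12 difference with a 95% CI and no p-value, on the Japan-only pain FAS for PAINS-pNF and the Japan-only FAS for PlexiQoL. Region drops out of the model, as 7.4 already provides. If the unstructured covariance does not converge, use the fallback sequence already specified in 4.2.2.1.5.
- Table 18: set the PlexiQoL row to Japan-only FAS.
- Table 19: move the whole-period waterfall and histogram to the China-only selumetinib FAS, and the PlexiQoL primary-analysis table to the China-only FAS.
- SAP 7.3, 8.3 and the model-table titles: name the Cycle 12 difference, with the period average as an additional output if wanted.

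The cost is edits to the output lists and two further Japan tables from programs that already exist for the global analysis. No new data are needed, and the testing procedure does not change.
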